5.3.4 Secondary objective

In order to describe the adherence to MTT24.5 the following metrics will be summarize:

- Mean number of days that participant completed on site program
- Mean number of training complementary exercises that participant completed at home.
- Percentage of subjects who completed the program

5.4 Handling of Missing, Unused, and Spurious Data

Variables with more than 20% of missing data will not be included in the analysis. For variables that have less than 20% of missing values, firstly it will be investigated and tried to complete the missing data. Available data will be included in the data listings and tabulations showing for each report the actual total. No imputation techniques will be used for missing data.

5.5 Confidence intervals and p-values

All applicable statistical tests will be 2-sided and will be performed using a 5% significance level. All confidence intervals presented will be 95% and two-sided.

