3.2 Study hypothesis

- *Hypothesis 1*

The MTT24.5 cognitive training program is associated with cognitive brain functional changes, as it may increase performance in memory and/or attention and/or verbal fluency and/or language and/or visuospatial skills in adults without clinical cognitive impairment or with subjective cognitive decline (SCD).

- *Hypothesis 2*

The MTT24.5 cognitive training program is associated with changes in brain neuroplasticity, as it may increase or modify the volume of specific brain areas and/or their level of activation.

- *Hypothesis 3*

The improvement in performance of the cognitive abilities listed in Hypothesis 1 is associated with changes in brain neuroplasticity.

- *Hypothesis 4*

Different baseline conditions may modulate responses to the cognitive program, including: a) baseline cognitive reserve, b) history of dementia, c) non-communicable chronic diseases, d) lifestyle habits, and e) medication use.

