3.3 Study objectives

- ***Primary objectives***

1. Evaluate the effects of MTT24.5 on cognitive abilities such as memory, attention, orientation, verbal fluency, language and visuospatial skills
2. Assess the effects of MTT24.5 on brain structural characteristics, considering brain volumes in globally standardized areas, as well as those associated with cognitive abilities.
3. Examine the effects of MTT24.5 on brain activation, defined as patterns of metabolism distribution and neuronal perfusion overall, and according to cognitive brain areas with taxonomic mapping.
4. Determine if there are response phenotypes based on the distribution of individual baseline characteristics, such as age, gender, lifestyle factors, medical history, medications, family history of dementia, diet, and baseline cognitive reserve score.

- ***Secondary objective***

Analyze the tolerance and adherence to MTT24.5, and its association with outcomes regarding cognitive variables, as well as structural and/or functional brain changes.

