5.3 Statistical analysis methods

5.3.1 Objective 1

The mean baseline ACE score and standard deviation (SD) will be reported for both the intervention and control groups. Additionally, the improvement from baseline to the end of the program will also be presented for each group.

To assess the impact of MTT24.5 on cognitive abilities, a linear model will be utilized for each cognitive domain (global, memory, attention and orientation, verbal fluency, language, and visuospatial skills). Each model will use the improvement score value as the outcome variable and the group (intervention and control) as the independent variable. The group term will evaluate the non-standardized intervention effect, indicating whether the mean improvement in scores (change from baseline) differs between the control and intervention groups. The effect size is defined as the difference between the mean improvement on the intervention group and the mean improvement on the control group.

To compute standardized effect sizes, Cohen's d Statistic will be calculated. Standardized metrics facilitate comparisons across different scores.

The fulfillment of model assumptions will be assessed, and if they are not met, proposals for improvement will be suggested.

5.3.2 Objective 2 and 3

For these objectives the subset of subjects within the intervention group who underwent BMRI will be considered. No control group is available for this assessment.

To evaluate the impact of MTT24.5 on brain volume and brain activation, a t-test will be conducted for each brain improvement outcome to determine whether the mean improvement differs from zero.

For each brain outcome, the non-standardized effect size will be reported as the mean improvement, while the standardized effect size will be calculated using the Cohen's d Statistic for repeated measures.

5.3.3 Objective 4

To identify potential response phenotypes based on individual baseline characteristics (including age, gender, medical history, medications, family history of dementia, and baseline cognitive reserve score), a linear model will be employed for each covariate of interest. The primary outcome will be modelled with the covariate of interest, the group variable, and their interaction. This interaction term will assess whether the intervention effect varies across covariate groups.

To summarize the results, a forest plot displaying the standardized effect size for each covariate group will be generated.

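### Primary objectives 2 and 3 rest on 17 brain tests, each at an unadjusted 5%, with no rule for which or how many results support the claim

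*SAP*

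**What the plan says.** SAP 3.3 lists two brain questions among the primary objectives. Objective 2 reads "Assess the effects of MTT24.5 on brain structural characteristics, considering brain volumes in globally standardized areas", and objective 3 reads "Examine the effects of MTT24.5 on brain activation, defined as patterns of metabolism distribution and neuronal perfusion overall". The matching Hypothesis 2 (SAP 3.2) says of the program that "it may increase or modify the volume of specific brain areas and/or their level of activation".

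SAP 3.9 lists the outcomes behind these objectives: 11 volume or thickness measures and 6 cingulate activation measures. It labels all 17 as secondary. SAP 4.2 confirms that this is the set considered.

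The analysis in SAP 5.3.2 is that "a t-test will be conducted for each brain improvement outcome to determine whether the mean improvement differs from zero". It uses only the imaging subset of the intervention group, without controls. SAP 5.5 sets the error level, "All applicable statistical tests will be 2-sided and will be performed using a 5% significance level", and adds "All confidence intervals presented will be 95% and two-sided". Tables 3 and 4 give each region its own p-value. The SAP has no adjustment, no testing order, no designated key region and no statement that these tests are exploratory.

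**The concern.** Seventeen chances to cross 5% are not one chance. Hypothesis 2 joins volume and activation with and/or and allows a change in either direction. The SAP does not say which results, or how many, would support it. A report could therefore cite one or two regions with p below 0.05 as evidence on a primary objective, and a reader would have no way to tell what error rate stands behind that statement. These comparisons also have no control group, so no comparator would help expose a chance finding.

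The same gap exists on a smaller scale for the cognitive domains, which Hypothesis 1 also joins with and/or. The total ACE score is the single primary outcome and is not touched.

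**Working it through.** **The plan's own figure.** The SAP gives no error rate or power for the brain tests. Its one power statement (SAP 3.7) concerns the score improvement, with 56 and 20 subjects, a difference of 4 and an SD of 5.4. The standard error is 5.4 × √(1/56 + 1/20) = 1.407, so the noncentrality is 4/1.407 = 2.84. Power at two-sided 5% is 80.1% by the noncentral t distribution. The stated minimum of 80% is reproduced, but it says nothing about the imaging outcomes.

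**Number of brain tests (SAP 3.9).**
- Volume or thickness: anterior cingulate 4, grey matter totals 3, middle frontal gyrus 4, total 11.
- Activation: anterior, medial and posterior cingulate, left and right, total 6.
- Together: 11 + 6 = 17.

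**If the tests are independent and nothing changes.** The chance of at least one p below 0.05 among k tests is 1 − 0.95^k.
- 17 tests: 1 − 0.95^17 = 58.2%, with 17 × 0.05 = 0.85 false positives expected.
- 11 volume or thickness tests: 43.1%.
- 6 activation tests: 26.5%.

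**If the tests are correlated.** The SAP gives neither the correlations nor the size of the imaging subset, so both are assumptions. One-sample t-tests were simulated with no true change, n = 30 and the same correlation between all 17 outcomes (at least 20,000 runs per setting). The last two columns show the chance of any rejection after Benjamini-Hochberg (BH) at 5%.

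| Common correlation | Unadjusted | BH, 17 pooled | BH, 11 and 6 separate, either family |
|---|---|---|---|
| 0 | 58% | 5.0% | about 9.5–10% |
| 0.2 | 54% | 4.7% | 9.3% |
| 0.5 | 39% | 4.2% | 7.4% |
| 0.7 | 28% | 3.5% | 5.9% |
| 0.9 | 15% | 2.6% | 3.7% |

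Assuming n = 15 or n = 56 instead moved the unadjusted figures by no more than about 1 to 2 points. A more realistic structure, with high correlation within a region and weaker correlation elsewhere, gave 52% falling to 27% as the correlations rose.

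**Cognitive domains.** With six domains, 1 − 0.95^6 = 26.5% if independent. With five, 1 − 0.95^5 = 22.6%. The SAP supports both counts: 5.3.1 treats attention and orientation as one domain, while 3.9, 4.2 and Table 2 separate them.

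**The case against.** The strongest reply is that SAP 3.9 calls all 17 outcomes secondary. SAP 4.1 and Table 2 name one primary outcome, and the power statement covers only the score. Leaving secondary outcomes unadjusted, with every result and interval shown, is common in a non-randomized study. The reply is fair as far as it goes, and a declared exploratory status would be an acceptable answer. The SAP does not make that declaration, however, and no other analysis addresses objectives 2 and 3, which it calls primary. The label alone does not settle the matter.

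Two stronger readings are tempting, and the documents do not support either.

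- A reader might infer that one significant region is enough to count Hypothesis 2 as supported. The and/or wording permits that reading, but the hypothesis is a scientific statement and not a decision rule, and the objectives say only that effects will be assessed and examined. What can be shown is that no rule exists.
- A reader might infer that a false brain effect is likely. That holds, in the sense of above 50%, only up to a common correlation of about 0.3. The list contains left and right sides of the same region, thickness and volume of the same gyrus, and cortical grey matter both in percent and in cm3. Strong correlation is therefore plausible, and the chance may be well below one half.

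It can also be said that only favourable changes would be claimed. The independent figure is then 1 − 0.975^17 = 35%, and about 14% to 29% with correlation blocks. That is smaller but still well above 5%.

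**Conclusion.** The point holds. Two primary objectives are answered only by 17 unadjusted tests, and the SAP does not say what pattern of results supports a claim. With no true change, the chance of at least one false positive is about 15% to 58%, or roughly 3 to 12 times the nominal 5%. Where it falls in that range depends on correlations that the SAP does not give. The figures assume two-sided one-sample t-tests, n = 30 and a common correlation from 0 to 0.9.

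The change should be made before analysis. It does not bear on the primary outcome, because the total ACE score is one test at 5%.

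**What to change.** In SAP 5.5:

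- Keep the total ACE score at 5% without adjustment.
- Apply Benjamini-Hochberg at 5% to the 17 brain p-values as one family. When nothing changes, the chance of any false claim is then about 3% to 5%. If structure and activation are kept as two families because they are separate objectives, state that the chance across both is about 4% to 10%.
- State what is being controlled. Benjamini-Hochberg controls the false discovery rate, and it controls family-wise error only when no region truly changes. If strict family-wise control is wanted, use Holm.
- Apply the same method to the cognitive-domain p-values, once SAP 5.3.1 has been reconciled with 3.9, 4.2 and Table 2 on whether attention and orientation are one domain or two.
- Show raw and adjusted p-values in Tables 2 to 4 and keep the effect sizes and 95% confidence intervals. State that a claim for a named region or domain needs an adjusted p below 0.05.

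If the sponsor regards the brain tests as exploratory, the SAP should say so explicitly and reconcile the primary-objective label in 3.3 with the secondary-outcome label in 3.9.

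The cost is a few sentences, one call to R's p.adjust per family and an extra table column. No new data are needed. The price is somewhat less power for any single region. The adjustment deals only with chance findings and does not make up for the missing control group.

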5.6 Statistical software employed

The statistical software R version 4.3.0 will be used for the analyses.

5.7 Reporting conventions

P-values ≥ 0.001 will be reported to 3 decimal places; p-values less than 0.001 will be reported as " <0.001 ". The mean, standard deviation, and any other statistics other than quantiles, will be reported to one decimal place greater than the original data. Quantiles, such as median, or minimum and maximum will use the same number of decimal places as the original data. Estimated parameters, not on the same scale as raw observations will be reported to 3 significant figures.

6. Dummy tables

Figure 1: Consort

[figure not shown]

Table 1. Socio-demographic characteristics by group

	Control group	Intervention Group	Intervention Group BMRI subset
	n/N (%)	n/N (%)	n/N (%)
Socio-demographic characteristics			
Sex			
Male			
Female			
Age*			
Age categorized			
<=65 years			
>65 years			
Years of education*			
Mediterranean diet	-		
Fruit consumption			
3 or more per day			
Less than 3 per day			
Vegetal consumption			
2 or more per day			
Less than 2 per day			
Nuts/seeds consumption			
3 or more per day			
Less than 3 per day			
Alcohol consumption			
Physical activity	-		
Clinical characteristics			
Cognitive reserve			
Low			
High			
Diabetes history			
Hypertension history			
Dyslipidemia history			
Myocardial infarction			
Previous cerebrovascular accident			
Sleep apnea syndrome			
Epilepsy			
Parkinson's disease			
Dementia family history			

*Mean and (SD) will be reported

** At least

Table 2. Effect of MTT 24.5 program on cognitive abilities outcomes

	Control group (N=)	Intervention Group (N=)	P-value
Primary Outcome			
Global cognitive ability			
Score at baseline, mean (\pm SD)			
Improvement from baseline, mean (\pm SD)			
Non-standardized effect size (95% CI)*			
Standardized effect size (95% CI)**			
Secondary Outcomes			
Attention cognitive ability			
Score at baseline, mean (\pm SD)			
Improvement from baseline, mean (\pm SD)			
Non-standardized effect size (95% CI)*			
Standardized effect size (95% CI)**			
Orientation cognitive ability			
Score at baseline, mean (\pm SD)			
Improvement from baseline, mean (\pm SD)			
Non-standardized effect size (95% CI)*			
Standardized effect size (95% CI)**			
Memory cognitive ability			
Score at baseline, mean (\pm SD)			
Improvement from baseline, mean (\pm SD)			
Non-standardized effect size (95% CI)*			
Standardized effect size (95% CI)**			
Verbal fluency cognitive ability			
Score at baseline, mean (\pm SD)			
Improvement from baseline, mean (\pm SD)			
Non-standardized effect size (95% CI)*			
Standardized effect size (95% CI)**			
Language cognitive ability			
Score at baseline, mean (\pm SD)			
Improvement from baseline, mean (\pm SD)			
Non-standardized effect size (95% CI)*			
Standardized effect size (95% CI)**			
Visuospatial skills cognitive ability			
Score at baseline, mean (\pm SD)			
Improvement from baseline, mean (\pm SD)			
Non-standardized effect size (95% CI)*			
Standardized effect size (95% CI)**			

Abbreviations: CI, confidence interval; SD, standard deviation

*Non-standardized effect size defined as the difference between the mean improvement on the intervention group and the mean improvement on the control group

**The standardized effect size defined as the difference between the mean improvement on the intervention group and the mean improvement on the control group, divided by the pooled standard error (Cohen's d Statistic)

Table 3. Effect of MTT 24.5 program on brain volume outcomes

	Intervention Group (N=)	P-value
Anterior cingulate gyrus right thickness		
Baseline value, mean (\pm SD)		
Non-standardized effect size (95% CI)*		
Standardized effect size (95% CI)**		
Anterior cingulate gyrus left thickness		
Baseline value, mean (\pm SD)		
Non-standardized effect size (95% CI)*		
Standardized effect size (95% CI)**		
Anterior cingulate gyrus right volume		
Baseline value, mean (\pm SD)		
Non-standardized effect size (95% CI)*		
Standardized effect size (95% CI)**		
Anterior cingulate gyrus left volume		
Baseline value, mean (\pm SD)		
Non-standardized effect size (95% CI)*		
Standardized effect size (95% CI)**		
Cerebrum grey matter total volume		
Baseline value, mean (\pm SD)		
Non-standardized effect size (95% CI)*		
Standardized effect size (95% CI)**		
Cortical Grey Matter volume (%)		
Baseline value, mean (\pm SD)		
Non-standardized effect size (95% CI)*		
Standardized effect size (95% CI)**		
Cortical Grey Matter volume (cm3)		
Baseline value, mean (\pm SD)		
Non-standardized effect size (95% CI)*		
Standardized effect size (95% CI)**		
Middle frontal gyrus right thickness		
Baseline value, mean (\pm SD)		
Non-standardized effect size (95% CI)*		
Standardized effect size (95% CI)**		
Middle frontal gyrus left thickness		
Baseline value, mean (\pm SD)		
Non-standardized effect size (95% CI)*		
Standardized effect size (95% CI)**		
Middle frontal gyrus right volume		
Baseline value, mean (\pm SD)		
Non-standardized effect size (95% CI)*		
Standardized effect size (95% CI)**		
Middle frontal gyrus left volume		
Baseline value, mean (\pm SD)		
Non-standardized effect size (95% CI)*		
Standardized effect size (95% CI)**		

Abbreviations: CI, confidence interval; SD, standard deviation

**Non-standardized effect size defined as the mean improvement on the intervention group

**The standardized effect size defined as the mean improvement on the intervention group divided by the standard error (Cohen's d Statistic)

Table 4. Effect of MTT 24.5 program on brain activation outcomes

	Intervention Group (N=)	P-value
Left anterior cingulate		
Baseline value, mean (\pm SD)		
Non-standardized effect size (95% CI)*		
Standardized effect size (95% CI)**		
Right anterior cingulate		
Baseline value, mean (\pm SD)		
Non-standardized effect size (95% CI)*		
Standardized effect size (95% CI)**		
Left medial cingulate		
Baseline value, mean (\pm SD)		
Non-standardized effect size (95% CI)*		
Standardized effect size (95% CI)**		
Right medial cingulate		
Baseline value, mean (\pm SD)		
Non-standardized effect size (95% CI)*		
Standardized effect size (95% CI)**		
Left posterior cingulate		
Baseline value, mean (\pm SD)		
Non-standardized effect size (95% CI)*		
Standardized effect size (95% CI)**		
Right posterior cingulate		
Baseline value, mean (\pm SD)		
Non-standardized effect size (95% CI)*		
Standardized effect size (95% CI)**		

Abbreviations: CI, confidence interval; SD, standard deviation

*Non-standardized effect size defined as the mean improvement on the intervention group

**The standardized effect size defined as the mean improvement on the intervention group divided by the standard error (Cohen's d Statistic)

Figure 2. Effect of MTT 24.5 program on cognitive abilities by covariates groups

Forest plot

7. References

